4.4 Immunogenicity

Serum samples for ADA assessments will be conducted utilizing a tiered approach (screen, confirm, titer), and ADA data will be collected at scheduled visits shown in the CSP. Blood samples collected outside of the protocolled window are summarized at the closest nominal time point that does not already have a value. ADA result from each sample will be reported as either positive or negative. If the sample is positive, the ADA titer will be reported as well. A participant is defined as being ADA-positive if a positive ADA result is available at any time, including baseline and all post-baseline measurements; otherwise ADA negative.

All participants who received at least 1 dose of study intervention with at least 1 reportable immunogenicity measurement will be included in the immunogenicity analysis set. The

number and percentage of ADA-evaluable participants that fall into the immunogenicity analysis set in the following categories will be provided by levels/cohorts:

- Anti-drug antibody (ADA) positive at baseline and/or post-baseline visits. The
 percentage of these participants in a population is known as ADA prevalence.
- Treatment-induced ADA positive (positive post-baseline and not detected at baseline).
- Treatment-boosted ADA positive (baseline ADA titer that was boosted greater than the variability of the assay (ie, ≥ 4-fold increase).
- Treatment-emergent ADA positive (either treatment-induced ADA positive or treatment-boosted ADA positive). The percentage of these participants in a population is known as ADA incidence.
- Participants who are treatment-emergent ADA negative (Participants who are ADA
 positive but not fulfilling the conditions for treatment-emergent ADA positive).
- ADA positive at baseline and at least one post-baseline assessment.
- ADA positive at baseline and not detected post-baseline.
- Persistent positive, defined as ADA negative at baseline and having at least 2
 post-baseline ADA positive measurements with ≥ 16 weeks between first and last
 positive, or an ADA positive result at the last available post baseline assessment. For
 studies less than 16 weeks in duration, only the last post-baseline requirement applies.
- Transient positive, defined as ADA negative at baseline and at least one post-baseline ADA positive measurement and not fulfilling the conditions for persistently positive.

The potential impact of ADAs on PK, pharmacodynamics, and safety will be assessed if data allow. These analyses will be described separately from the SAP and presented separately from the main CSR

4.5 Safety Endpoints Analyses

The domain safety covers exposure, AEs, clinical laboratory, vital signs, electrocardiograms (ECGs), echocardiograms, ECOG performance status and B-symptoms.

Tables will be provided for the safety analysis set, listings are provided for all participants or the safety analysis set depending on the availability of data.

All safety analysis will be presented by dose level/cohort.

4.5.1 Exposure

4.5.1.1 Definitions and Derivations

- Duration of exposure is defined by the last date of actual dosing (ie, a dose > 0 mg was given) in the last cycle plus 21 days minus the date of first treatment study intervention plus 1.
 - For participants who die whilst on study treatment or if a DCO occurs, duration
 of exposure is defined as date of death/DCO (whichever occurs first) minus the
 date of first treatment plus 1 day.
 - Therefore: Duration of exposure (weeks) = [min(last dose date where dose > 0 mg + 21 − 1, date of death, date of DCO) − first dose date + 1]/7.
- The duration of exposure in cycles is calculated as:

Duration of exposure (cycles) = the number of cycles in which at least one portion of intervention was administered (ie, dose > 0 mg). If a cycle is prolonged due to toxicity, this is still counted as one cycle.

- Actual duration of exposure is the number of sabestomig doses administered (ie, a dose >0mg was given) multiplied by 21 days (due to the fact that sabestomig as ordinarily dosed on every 3 weeks schedule).
 - Therefore: Actual duration of exposure in weeks (weeks) = the number of sabestomig doses administered multiplied by 3.
- Dose intensity of study intervention is addressed by considering relative dose intensity (RDI), where RDI is the percentage of the actual dose delivered relative to the intended dose through to treatment discontinuation. More specifically, RDI is defined as follows:
 - RDI = 100% × d/D, where d is the actual cumulative dose delivered up to the
 actual last day of dosing and D is the intended cumulative dose up to the actual last
 day of dosing. D is the total dose that would be delivered, if there were no
 modification to dose or schedule.
- Duration of treatment cycle delays will be derived for treatment cycles indicated as being
 delayed on the eCRF. For each individual dose, the duration of treatment cycle delay is the
 number of days the dose was received outside of the original planned dosing schedule.
 Overall duration of treatment cycle delays will be calculated as the sum of all individual
 treatment cycle delays during the study. For example, assume the eCRF indicate that there
 was a treatment cycle delay (question "Treatment cycle delayed" indicated as "Yes" by
 investigator) then the duration of the individual delay will be [date first dose received after

delay – date last dose received before delay – 21]. For example, if dose is given on days 1 and 24 with the eCRF indicating a delay, the duration of the delay = 24 - 1 - 21 = 2 days.

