#### 6.6.8 Dose Modification and Toxicity Management

If a participant experiences a clinically significant and/or unacceptable toxicity including a DLT not attributable to the disease or disease-related processes under investigation, dosing will be interrupted, and supportive therapy will be administered.

All toxicities will be graded according to NCI CTCAE v5.0.

The following general guidance should be followed for management of toxicities:

- Treat each of the toxicities with maximum supportive care (including withholding the agent suspected of causing the toxicity if required).
- If the symptoms promptly resolve with supportive care, consideration should be given to resuming the assigned study intervention along with appropriate continuing supportive care. If medically appropriate, dose modifications (eg, dose interruption) are permitted.
- All dose modifications (eg, dose interruption, discontinuation) should be documented with clear reasoning and documentation of the approach taken.
- Dose reductions are not permitted.

Toxicity Management Guidelines have been developed to assist Investigators with the recognition and management of toxicities associated with use of the IC inhibitor sabestomig. The TMGs are provided in Appendix I.

These TMGs are applicable to the management of participants receiving sabestomig as specified in the CSP. The TMGs provide information for the management of immune-mediated reactions, IRRs, and non-immune-mediated reactions that may be observed with monotherapy or combination checkpoint inhibitor regimens, with specific instructions for checkpoint inhibitor-specific dose modifications (including permanent discontinuation) and treatment interventions. Investigators are advised however to use local practice guidelines and consult local references for the management of toxicities observed with other anticancer treatment.

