## 6.7 Dose Delay

In the event of treatment-related toxicities, study intervention should be permanently discontinued if sabestomig is not given for more than 12 weeks.

If treatment interruption is caused by intercurrent illness that is not a direct consequence of sabestomig-related toxicity (ie, COVID-19 infection), the option to restart treatment can be offered beyond 12 weeks following discussion with the AstraZeneca representative. In the event of a COVID-19 infection, the investigator should use their judgment to delay treatment with sabestomig depending on the clinical situation of the participant.

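### SAP 4.5.1.1: actual exposure is not cut at death or data cut-off, and relative dose intensity and delay duration leave out a final hold that ends in discontinuation

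*SAP*

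**What the plan says.** All the derivations are in SAP 4.5.1.1.

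- **Total duration of exposure.** For participants who die on treatment, or when a DCO occurs, duration "of exposure is defined as date of death/DCO (whichever occurs first) minus the" first treatment date plus one day. The weekly formula takes the earliest of last dose + 20 days, death and DCO.
- **Actual duration of exposure.** "Actual duration of exposure is the number of sabestomig doses administered (ie, a dose >0mg was given) multiplied by 21 days"; in weeks it is the number of "sabestomig doses administered multiplied by 3". It has no death or DCO term.
- **RDI.** The lead sentence compares the dose delivered with the intended "dose through to treatment discontinuation. More specifically, RDI is defined as follows". In the formula that follows ("actual last day of dosing and D is the intended cumulative dose up to the actual last"), d for dose delivered and D for dose intended both stop at the final dose. D assumes no change to dose or schedule.
- **Delay duration.** For a cycle flagged as delayed, "the duration of the individual delay will be [date first dose received after" the delay, minus the date of the last dose before it, minus 21 days.

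SAP 4.5.1.2 commits to descriptive summaries of exposure in weeks and cycles, dose intensity and delay duration. Protocol 6.6.8 states that "Dose reductions are not permitted". Protocol 6.7 adds that, for treatment-related toxicity, "study intervention should be permanently discontinued if sabestomig is not given for more than 12 weeks".

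**The concern.** Actual exposure should not be longer than total exposure. Because only total is cut at death or DCO, following the rules as written can produce that result, and the study has several planned cut-offs at which some participants may still be on treatment.

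For RDI, the lead sentence and the formula name different end points. They differ whenever at least one planned dose falls between the last dose given and the discontinuation date. With dose reductions barred, holds and delays are the main way that RDI falls, yet a hold with no later dose enters neither RDI nor delay duration. What is at stake is a fair description of how far the three-weekly schedule was delivered, by dose level and cohort.

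**Working it through.** **Inputs.** The planned interval is 21 days (SAP 4.5.1.1). Twelve weeks is 84 days (Protocol 6.7) and is used as the illustrative gap. For total duration I use the SAP's weekly formula; the accompanying prose gives one day more when neither death nor DCO intervenes.

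**The SAP's own figure.** Doses on Days 1 and 24: 24 − 1 − 21 = 2 days of delay, as the SAP states. As a baseline check, one dose with no death or DCO gives total 21/7 = 3.0 weeks and actual 1 × 3 = 3.0 weeks, so the two measures agree.

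**Part 1: actual against total.** Take n doses on schedule from Day 1, with death or DCO k days after the last dose (k from 0 to 20).

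- Total days = 21(n − 1) + k + 1
- Actual days = 21n
- Excess = 20 − k days: 20 at k = 0, 1 at k = 19, none at k = 20

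| Doses (days) | Death or DCO | Total, weeks | Actual, weeks | Actual − total, days |
|---|---|---|---|---|
| 1, 22, 43, 64 | DCO Day 66 | 66/7 = 9.4 | 12.0 | 84 − 66 = 18 |
| 1, 22, 43, 64 | DCO Day 64 | 64/7 = 9.1 | 12.0 | 84 − 64 = 20 |
| 1 | Death Day 5 | 5/7 = 0.7 | 3.0 | 21 − 5 = 16 |
| 1, 21 | Neither | 41/7 = 5.9 | 6.0 | 42 − 41 = 1 |
| 1, 22, 106 | Neither | 126/7 = 18.0 | 9.0 | 63 − 126 = −63 |

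The fourth row shows that a dose one day early gives a small excess without any death or DCO. The last row shows the offset: total includes delay time and actual does not.

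**Part 2: RDI and delay.** RDI = 100 × doses given / three-weekly doses due by the end point, assuming full doses at one dose level.

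| Doses (days) | What follows | RDI by SAP formula | Delay by SAP formula | RDI to discontinuation |
|---|---|---|---|---|
| 1, 22, 106 | Restarts after 84 days | 3/6 = 50% | 106 − 22 − 21 = 63 days | Depends on later dosing |
| 1, 22 | Stops, Day 106 | 2/2 = 100% | 0 | 2/5 = 40%, or 2/6 = 33% if the Day 106 dose counts |
| 1, 22 | Stops, Day 50 | 2/2 = 100% | 0 | 2/3 = 67% |
| 1, 22, 64, 85 | Stops, Day 169 | 4/5 = 80% | 64 − 22 − 21 = 21 days | 4/8 = 50%, or 4/9 = 44% if the Day 169 dose counts |

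The unreported final hold is 106 − 22 − 21 = 63 days in the second row and 50 − 22 − 21 = 7 days in the third. The last row shows that an earlier delay still counts and only the final hold is lost.

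**The case against.** Several points on the other side have force.

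- **There is one formula.** The general RDI sentence is followed by a more specific definition, so a programmer has a rule to follow. SAP 4.5.2.1 also counts the 90 days from last dose in one phase and from discontinuation in the adjoining phase, as if the dates were the same. This stands as far as it goes: ending RDI at the last dose is a defensible choice. But the lead sentence still says something else, and the two dates separate after a hold.
- **Discontinuation is reported elsewhere.** Disposition (SAP 4.1.1.2) and adverse events leading to discontinuation (SAP 4.5.2.2) are tabulated. This stands, and it limits the consequence. Neither table gives the length of the final hold.
- **The outputs are descriptive.** SAP 4.5.1.2 does not name actual duration among its summaries, and SAP 5 says that interim outputs concentrate on response. Part 1 may therefore never reach a table.

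The documents also do not support some stronger readings that a reader might infer:

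- That RDI can fall only through holds or delays. Infusions may be interrupted (Protocol 6.2.1.2), so a partial dose lowers it too.
- That RDI favours those who tolerated the drug worst. At best they tie at 100% with participants who had no delay.
- That actual exceeds total for nearly everyone still on treatment at a cut-off. Earlier delays can remove or reverse the excess.

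**Conclusion.** Both defects are real and minor.

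1. Actual duration can exceed total by 1 to 20 days for an on-schedule participant whose death or DCO falls within 19 days after the last dose. Accumulated delay reduces or reverses the excess.
2. RDI and delay duration omit a final hold that ends in discontinuation. In the 84-day illustration the SAP formula gives 100% and 0 days, against 33% to 40% and 63 days when the hold is counted. RDI is exactly 100% only if there was no earlier delay and no missed or partial dose.

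The effect on a cohort mean cannot be established from the documents. Suppose 10% of participants stop after 3 doses and 1 missed dose: 10% × (1 − 3/4) = 2.5 points. Suppose 25% stop after 3 doses and 3 missed doses: 25% × (1 − 3/6) = 12.5 points. That range is illustrative only. The 25% limit in Protocol 4.5 concerns all treatment-related discontinuations of any grade and is not a rate of stopping after a hold. No primary endpoint, futility rule or safety pause criterion uses these outputs.

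**What to change.** 1. **Actual duration.** Define it as the sum over doses of the smallest of 21 days, days to the next dose, and days to death or DCO counted inclusively (date minus dose date + 1). It then cannot exceed total duration. Four doses with DCO on Day 66 give 21 + 21 + 21 + 3 = 66 days, and death on Day 5 gives 5 days; both equal total.
2. **RDI and delay.** Choose one end point for D and match the lead sentence to it.
   - Either run D to the end-of-intervention date, death or DCO, whichever is first, and state whether a dose due on that date counts.
   - Or keep the last day of dosing, delete the reference to discontinuation, and summarize separately the final holds with no later dose: end-of-intervention date minus last dose date minus 21, if positive.

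The cost is SAP wording and programming. SAP 4.2.7.2 already lists the dosing and end-of-intervention dates as eCRF items. The first RDI option has two drawbacks: reported RDI may be lower for participants who stop after a hold, and it also counts gaps unrelated to tolerability, such as a lag before discontinuation for progression is recorded.

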4.5.1.2 Presentation

Duration of exposure to study intervention in weeks and cycles will be summarized by descriptive statistics. Dose intensity and duration of treatment cycle delays will be summarized by descriptive statistics. Exposure to IP, ie, total amount of study drug received will be listed for all participants. Exposure swimmer plot(s) may be produced, with a line presented for each participant to display relevant exposure and disposition details.

Dosing deviations for study intervention will be summarized with reasons for deviations for the following category: treatment cycle delays. Dosing delays will be derived based on the scheduled dosing dates using the previous dose given as reference. Treatment cycle delays will be summarized.

Analysis of treatment cycle delays may be performed if greater than 20% of participants experience a treatment cycle delay.

4.5.2 Adverse Events

4.5.2.1 Definitions and Derivations

The MedDRA (using the latest or current MedDRA version) will be used to code AEs. AEs will be graded according to the National Cancer Institute Common Terminology Criteria for AEs (CTCAE) (using the CTCAE version 5.0).

Treatment emergent adverse events (TEAEs) are all AEs which onset or worsen in severity following the first administration of IP within the duration of the treatment period, up to and including 90 days after the last dose of study treatment as per the study safety follow-up period but prior to subsequent cancer therapy. Worsening in severity (intensity) is determined by comparison with the pre-treatment CTCAE grade of the AE recorded closest to the start of dosing.

When assigning AEs to the relevant phase of the study, the following rules apply and any deviations must be agreed by the study team:

- Pre-treatment phase: All AEs with a start date after signing the informed consent form, but before the first dose of study treatment that do not subsequently go on to worsen during the treatment emergent phase.
- Treatment emergent phase: All AEs (starting or worsening) on or after the first dose of study intervention and within 90 days post-treatment safety follow-up after last dose of study treatment or but prior to subsequent cancer therapy, whichever occurs first.

 Post-treatment phase: All AEs starting more than 90 days after discontinuation of study treatment or on or after the initiation of subsequent anti-cancer therapy, whichever occurs first.

For rules on missing or partial dates, see Section 3.3.6.

Serious Adverse Events (SAEs)

A serious adverse event (SAE) is any AE that:

- Results in death
- Is immediately life-threatening
- Requires inpatient hospitalization or prolongation of existing hospitalization
- Results in persistent or significant disability/incapacity
- Is a congenital anomaly/birth defect in offspring of the participant
- Is an important medical event that may jeopardize the participant or may require medical treatment to prevent one of the outcomes listed above

AEs of special interest

An adverse event of special interest (AESI) is one of scientific and medical interest specific to understanding of the IP and may require close monitoring and rapid communication by the investigator to the sponsor. The AESIs for sabestomig include events with a potential inflammatory or immune-mediated mechanism and which may require more frequent monitoring and/or interventions such as steroids, immunosuppressants and/or hormone replacement therapy. Additionally, IRRs and events of similar presentation are considered AESIs for sabestomig. These AESIs are being closely monitored in clinical studies with sabestomig.

An immune-mediated adverse event (imAE) is defined as an AESI that is associated with drug exposure, is consistent with an immune-mediated mechanism of action and has no clear alternate etiology. Serologic, immunologic, and histologic (biopsy) data, as appropriate, should be used to support an imAE diagnosis. Appropriate efforts should be made to rule out neoplastic, infectious, metabolic, toxin, or other etiologic causes of the imAE.

The imAEs that may be observed with sabestomig (based on the available nonclinical and clinical data, review of the cumulative literature, reported toxicities for the same class of

agents, and biological plausibility) and are considered AESIs for this study include, but are not limited to:

- Respiratory disorders: Pneumonitis, ILD
- Gastrointestinal disorders: Non-infectious diarrhea, colitis, including bowel perforation, hematochezia, and ileus
- Endocrinopathies: Hyperthyroidism and hypothyroidism (including thyrotoxicosis), adrenal insufficiency, diabetes mellitus, pituitary inflammation (hypophysitis), and hyperpituitarism and hypopituitarism
- · Hepatic disorders: Elevated transaminases and hepatitis
- Renal disorders: Nephritis, nephropathy, elevated serum creatinine, acute renal/kidney injury, and glomerulonephritis/sclerosis
- Cardiac disorders: Myocarditis, pericarditis, bradycardia, tachycardia, arrhythmia, ischemia, heart failure, and acute coronary syndrome
- Skin disorders: Rash, pruritus, dermatitis, vitiligo, psoriasis, SJS/TEN, bullous pemphigoid, and lichenoid dermatitis
- Other rare imAEs including encephalitis, hemophagocytic lymphohistiocytosis, encephalitis, lymphocytosis, myositis/polymyositis, uveitis, iridiocyclitis, uritis, arthritis, Guillain-Barre syndrome, myasthenia gravis, vasculitis, hemolytic anemia, aplastic anemia, and sarcoidosis

Other AEs which are considered to be AESIs with sabestomig include, but are not limited to:

- Infusion-related reactions; hypersensitivity including anaphylactic/anaphylactoid and other allergic reactions
- Immune complex disease and vasculitis
- Cytokine release syndrome; tumor lysis syndrome

Other categories may be added, or existing terms may be modified as necessary. An AstraZeneca medically qualified expert after consultation with the Global Patient Safety Physician has reviewed the AEs of interest and identified which higher-level terms and which preferred terms contribute to each AESI. Further reviews may take place prior to database lock to ensure any further terms not already included are captured within the categories. Preferred terms used to identify AESIs will be listed prior to database lock.

Other significant adverse events (OAE)

No OAEs are planned to be defined for this study.

4.5.2.2 Presentation

All TEAEs will be summarized and listed. AEs which are not treatment emergent will only be listed based on safety analysis set.

TEAEs will be counted once for each participant for calculating percentages of participants experiencing TEAEs. In addition, if the same TEAE occurs multiple times within a particular participant, the highest severity and level of relationship observed will be reported. For tables by MedDRA system organ class (SOC) and MedDRA preferred term (PT), participants with multiple TEAEs will be counted once for each SOC/PT.

An overall summary table of the number of participants experiencing each category of AEs will be produced. The number of participants experiencing TEAEs by MedDRA SOC and PT will be summarized and the type of incidence, severity, and relationship to IP will be summarized. Further splits by CTCAE grade, causal relationship to IP and AEs with Grade 3 or higher will also be also summarized.

Separate tables will present dose limiting toxicities, AEs leading to discontinuation, SAEs, IP-related adverse events

Details of any deaths will be summarized and listed. AEs leading to death are also summarized

SAEs

SAEs will be summarized as described above for the TEAEs.

AEs of special interest

Grouped summary tables of certain MedDRA PTs will be produced and may also show the individual PTs which constitute each AESI grouping. Groupings will be based on PTs provided by the medical team prior to database lock, and a listing of the PTs in each grouping will be provided.

Summaries of the above-mentioned grouped AE categories include number and percentage (%) of participants who have:

- At least one AESI presented by event outcome
- At least one AESI causally related to IP

At least one AESI leading to discontinuation of study intervention

A summary of total duration (days) of AESI will be provided for events which have an end date, and this may be supported by summaries of ongoing AESIs at death and, separately, at data cut-off.

ImAEs

ImAEs will be summarized as described above for the TEAEs.

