#### 8.3.2 Follow-up of AEs and SAEs

Any AEs that are unresolved at the participant's last AE assessment in the study are followed up by the Investigator for as long as medically indicated, but without further recording in the eCRF. AstraZeneca retains the right to request additional information for any participant with ongoing AE(s)/SAE(s) at the end of the study, if judged necessary.

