Endocrinopathy (eg, hyperthyroidism, thyroiditis, hypothyroidism, type 1 diabetes mellitus, hypophysitis, hypopituitarism, and adrenal insufficiency)	Any Grade (Depending on the type of endocrinopathy, refer to NCI CTCAE applicable version in study protocol for defining the CTC grade/severity)	General Guidance	
 
For Any Grade
 
Consider consulting an endocrinologist for endocrine events.
 
Consider discussing with study physician, as needed.
 
Monitor patients for signs and symptoms of endocrinopathies. Non-specific symptoms include headache, fatigue, behaviour changes, mental status changes, photophobia, visual field cuts, vertigo, abdominal pain, unusual bowel habits, polydipsia, polyuria, hypotension, and weakness.
 
Patients should be thoroughly evaluated to rule out any alternative etiology (eg, disease progression including brain metastases, or infections).
 
Depending on the suspected endocrinopathy, monitor and evaluate thyroid function tests: TSH, free T3 and free T4 and other relevant endocrine and related labs (eg, blood glucose and ketone levels, HgA1c).If a patient experiences an AE that is thought to be possibly of autoimmune nature (eg, thyroiditis, pancreatitis, hypophysitis, or diabetes insipidus), the Investigator should send a blood sample for appropriate autoimmune antibody testing.
 

Adverse Events	Severity Grade of the Event	Dose Modifications	Toxicity Management
			
 
Investigators should ask participants with endocrinopathies who may require prolonged or continued hormonal replacement, to consult their primary care physicians or endocrinologists about further monitoring and treatment after completion of the study.
 

	Grade 1	No dose modifications.	For Grade 1
			
 
Monitor patient with appropriate endocrine function tests.
 

			
 
For suspected hypophysitis/hypopituitarism, consider consulting an endocrinologist to guide assessment of early-morning ACTH, cortisol, TSH and free T4; also consider gonadotropins, sex hormones, and prolactin levels, as well as cosyntropin stimulation test (though it may not be useful in diagnosing early secondary adrenal insufficiency).
 

			
 
If TSH < 0.5 x LLN, or TSH > 2 x ULN, or consistently out of range in 2 subsequent measurements, include free T4 at subsequent cycles as clinically indicated and consider consultation of an endocrinologist.
 

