3.3.6 Missing Dates

When partial dates exist in the data there are some general conventions to be applied when the month or day are missing. These are described in the PHUSE guidance on partial dates, which are outlined below:

If the whole date is missing, it is more difficult to follow a general principle and these are reviewed within the study and decided on how to be handled. General guidance for completely missing dates are provided below, but the guidance is assessed as necessary within the study.

Generally, the imputation of dates is used to decide if an observation is treatment emergent for adverse events (AEs) or concomitant medications. The imputed dates should not be used to calculate durations, where the results would be less accurate.

The following are the guidelines used when partial dates are detected in the study:

- For missing diagnostic dates (eg,: disease diagnosis), if day and/or month are missing use
 01 and/or Jan. If year is missing, put the complete date to missing.
- For missing AE and concomitant medication start dates, the following is applied:
 - a. Missing day impute the 1st of the month unless month is the same as month of the first dose of study drug then impute first dose date.
 - b. Missing day and month impute 1st January unless year is the same as first dose date then impute first dose date.

- c. Completely missing impute first dose date unless the end date suggests it could have started prior to this in which case impute the 1st January of the same year as the end date.
- Imputed start date should be no later than the end date.
- For missing AE and concomitant medication end dates, the following is applied:
 - a. Missing day impute the last day of the month unless both the month and the year are the same as the last dose date or the analysis data cut-off date then impute the last dose date or the analysis data cut-off date.
 - b. Missing day and month impute 31st December unless the year is the same as the last dose date or the analysis data cut-off date then impute the last dose date or the analysis data cut-off date.

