 - c. Completely Missing need to look at whether the AE/medication is still ongoing before imputing a date and also when it started in relation to study drug. If the ongoing flag is missing then assume that AE is still present / medication is still being taken (ie, do not impute a date). If the AE/medication has stopped and start date is prior to first dose date then impute first dose date. Or if it started on or after first dose date then impute to the last dose of study drug date + 1.
- Flags are retained in the database indicating where any programmatic imputation has been applied, and in such cases for AEs and concomitant medications, any durations would not be calculated.
- If a participant is known to have died where only a partial death date is available then the
 date of death is imputed as the latest of the last date known to be alive +1 from the
 database and the death date, using the available information provided and applying the
 following:
 - For Missing day only using the 1st of the month.
 - For Missing day and Month using the 1st of January.

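### AESI duration is summarised only for events with an end date, so the figure runs short for persistent immune-mediated events

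*SAP*

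**What the plan says.** SAP 4.5.2.2 (Presentation, AEs of special interest) sets the rule: "A summary of total duration (days) of AESI will be provided for events which have an end date". The sentence goes on: "and this may be supported by summaries of ongoing AESIs at death and, separately, at data cut-off". The same section plans participant counts under the item "At least one AESI presented by event outcome", and for all treatment-emergent events it says "All TEAEs will be summarized and listed".

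Three other places decide which events have an end date:

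- Protocol 8.3.1 collects AEs until 90 days after the last dose, and SAEs until the end of the study.
- Protocol 8.3.2 says that AEs unresolved at the last AE assessment are "followed up by the Investigator for as long as medically indicated, but without further recording in the eCRF".
- SAP 3.3.6 keeps imputed dates out of durations: "The imputed dates should not be used to calculate durations, where the results would be less accurate", and "in such cases for AEs and concomitant medications, any durations would not be calculated".

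SAP 3.3.1 uses Kaplan-Meier for time-to-event variables where appropriate. It is not named for AESI duration.

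**The concern.** An event enters the duration summary only if it resolved before recording stopped. A short event passes that filter more often than a long one, so the average or median of those that pass is too low. Protocol 8.3.2 makes this systematic, because a resolution after the last AE assessment is normally not recorded.

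The effect should be greatest for the AESIs expected to persist. The AESI list includes hypothyroidism, adrenal insufficiency, diabetes mellitus and hypopituitarism, and Protocol Appendix I (Specific Immune-Mediated Reactions) refers to participants with "endocrinopathies who may require prolonged or continued hormonal replacement". Such events may never contribute a duration. A reader of the clinical study report would probably take the figure as time to resolution, and so see persistent toxicity as shorter than it is.

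**Working it through.** The plan gives no duration, resolution rate or expected number of AESIs, so there is no figure to reproduce. What follows is an illustration on assumed inputs.

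**Assumptions.** Resolving events have exponential durations with median m, so the rate is λ = ln 2 / m. A share p never resolves. The time from onset to the end of recording is uniform on (a, b), and G(t) is the probability that it is at least t.

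**True median over all events.** Solve (1 − p)·exp(−λt) + p = 0.5, which gives t = −ln[(0.5 − p)/(1 − p)] / λ. For m = 60 and p = 0.3: λ = 0.01155, (0.2/0.7) = 0.2857, and t = 1.2528/0.01155 = 108 days.

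**Median under the SAP rule.** The density of events that get an end date is proportional to λ·exp(−λt)·G(t). The share p cancels, so however many events never resolve, the reported median does not move.

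**Share left out.** With a = 0, the share of resolving events still open is (1 − exp(−λb))/(λb). For m = 60 and b = 240: λb = 2.773 and (1 − 0.0625)/2.773 = 34%. With p = 0.3 it becomes 0.3 + 0.7 × 0.338 = 54%.

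| Recording after onset (days) | m | p | True median | Median, events with end date | Left out |
|---|---|---|---|---|---|
| 90–365 | 14 | 0 | 14 | 14 | 0.1% |
| 90–365 | 30 | 0 | 30 | 29 | 2% |
| 90–365 | 60 | 0 | 60 | 51 | 11% |
| 90–365 | 90 | 0 | 90 | 65 | 21% |
| 90–365 | 90 | 0.2 | 127 | 65 | 37% |
| 30–180 | 90 | 0 | 90 | 40 | 47% |
| 0–240 | 14 | 0 | 14 | 13 | 8% |
| 0–240 | 60 | 0 | 60 | 38 | 34% |
| 0–240 | 120 | 0 | 120 | 51 | 54% |
| 0–240 | 60 | 0.3 | 108 | 38 | 54% |
| 0–240 | 120 | 0.3 | 217 | 51 | 68% |

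In the 0–240 rows with m of 60 or more, the truth moves from 60 to 217 days while the reported figure moves only from 38 to 51.

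**Kaplan-Meier on the same kind of data.** In simulations of 200,000 events with ongoing events censored, it returned the true median to within about 1 day wherever the median was reached. For example, it gave 90 for a true 90, and 126.5 for a simulated true 126.5. Where about 66% or more were ongoing it was not reached, while the end-date rule still gave 40 to 87 days.

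**Small groups.** With 10 to 30 events and 0–240 days of recording, I ran 10,000 repetitions per case. At a true median of 108 days the Kaplan-Meier median was not reached in 14 to 28% of runs. At 217 days it was not reached in 52 to 55%; when reached it centred on 125 to 158 days, against 51 days under the SAP rule.

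**The case against.** A reader might infer that the plan discards the longest AESIs. The documents do not support that. Ongoing events leave one descriptive statistic but stay in the report: counts by outcome are planned, all treatment-emergent events are listed, and the same sentence provides for summaries of ongoing AESIs. Nor are the omitted events always the longest. An event can lack an end date because it began shortly before death or data cut-off, or can have no duration because a date is partial. In the simulated long-event scenarios with 30–180 days of recording, 8 to 14% of ongoing events had run for less time than the median resolved event.

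A reader might also infer that an unresolved event can never be given an end date. Protocol 8.3.1 leaves at least 90 days of AE collection after an on-treatment onset unless death, withdrawal or cut-off intervenes, and it collects SAEs to the end of the study. Protocol 8.3.2 also lets the sponsor request further information on ongoing events. This argues against the 0–240 day rows as a general case. They are not excluded, however: Protocol 9.4.1 allows the Part B primary analysis from 3 months after the last participant's first dose, so late onsets can have little recorded follow-up.

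Finally, AESI duration is not a listed primary or secondary endpoint (Protocol Section 3). No hypotheses are tested (Protocol 9.1), and the numerical stopping limits in Protocol 4.5 rest on incidence. The limits of Kaplan-Meier in small groups are real, and censoring at death treats a competing outcome as uninformative.

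All of this stands and lowers the weight of the point. It does not remove the bias: the ongoing-event summaries are optional, and neither counts nor listings correct a duration.

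**Conclusion.** The AESI duration figure, as specified, is biased short. The direction follows from the rule itself. The size depends on how long AESIs last, what share never resolve and how long recording runs after onset, none of which the documents give. Over the assumed range the bias is negligible for events of about two weeks with at least 90 days of recording, which plausibly covers infusion reactions. It reaches a factor of two to four where many events persist (127 shown as 65 days; 217 shown as 51). An inference that a main tolerability result or a trial decision is distorted would go too far: this is a descriptive safety summary that no stated decision uses. Severity is minor, and the change is a cheap improvement. A median reported as not reached in a small group is less misleading than a short finite one.

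**What to change.** In SAP 4.5.2.2, replace the restriction to events with an end date by time to resolution, summarised by AESI group:

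- Use Kaplan-Meier over all AESIs in the group, censoring ongoing events at the last AE assessment or data cut-off, whichever is earlier.
- Report AESIs ongoing at death separately, or treat death as a competing event.
- State the median as not reached where that applies. Only list groups with few events, using a minimum number fixed in advance. Any confidence interval should allow for repeat events in one participant.
- Make the summaries of ongoing AESIs at death and at data cut-off mandatory.
- Beside every duration figure, show the number and percentage of events ongoing or without a usable end date. Events known to have resolved but with a partial date belong in that count and should not be censored as ongoing.

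The cost is revised SAP wording and one table. Onset, end, death and cut-off dates are already collected. The downside is imprecise or unreached medians in small groups.
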